7.2.4. End of Treatment

The patient will return to the clinical research facility at Week 144 (Visit 13) for the End-of-Treatment visit. If the patient discontinues prematurely (ie, before Week 144), and the procedures that would normally be performed at Week 144 should be performed as a Premature-Discontinuation Visit before the patient leaves the study. If the patient terminates the study early because ataluren is commercially available in that country then the patient does not need to come in for the 6-week Post-Treatment Follow-up Visit.

7.2.5. Post-Treatment Visits

All patients who discontinue study drug, except patients switching to commercial ataluren, must return for a Post-Treatment Visit at the investigator site 6 weeks (± 7 days) after the last dose of study drug and the End of Treatment Visit, for final study-related evaluations. If the End-of-Treatment Visit occurs >6 weeks after the last dose of study drug, the Post-Treatment Visit does not need to be performed.

7.3. Informed Consent

The investigator or sub-investigator must inform each prospective patient of the nature of the study, explain the potential risks, and obtain written informed consent/assent from the patient and/or the parent/legal guardian prior to performing any study-related screening procedures. Patients will be re-consented with the appropriate age-related documents as needed, if required by local regulations.

7.4. Vital Signs

Vital signs (including systolic and diastolic blood pressure, pulse rate, and body temperature) will be monitored at Screening/Baseline on Visit 1, Week 12 (Visit 2), Week 24 (Visit 3), Week 36 (Visit 4), Week 48 (Visit 5), Week 60 (Visit 6), Week 72 (Visit 7), Week 84 (Visit 8), Week 96 (Visit 9) Week 108 (Visit 10), Week 120 (Visit 11), Week 132 (Visit 12), Week 144 (Visit 13- End-of-Treatment/Premature Discontinuation), and at the Post-Treatment visit (6 weeks post discontinuation of study drug). The pulse rate and blood pressure determinations will be performed with the patient in a sitting position after a 5-minute rest.

7.5. Height, Weight, and Physical Examination

Standing height (in cm) will be measured at Screening/Baseline on Visit 1, Week 12 (Visit 2), Week 24 (Visit 3), Week 36 (Visit 4), Week 48 (Visit 5), Week 60 (Visit 6), Week 72 (Visit 7), Week 84 (Visit 8), Week 96 (Visit 9) Week 108 (Visit 10), Week 120 (Visit 11), Week 132 (Visit 12), Week 144 (Visit 13- End-of-Treatment/Premature Discontinuation), and at the Post-Treatment visit (6 weeks post discontinuation of study drug).

For nonambulatory patients, due to the difficulty in obtaining an accurate standing height measurement, ulna length and arm span will be used as a surrogate measure for height (see Study Manual). Ulna length and arm span (in cm) will be measured at Screening/Baseline on Visit 1, Week 12 (Visit 2), Week 24 (Visit 3), Week 36 (Visit 4), Week 48 (Visit 5), Week 60 (Visit 6), Week 72 (Visit 7), Week 84 (Visit 8), Week 96 (Visit 9) Week 108 (Visit 10), Week 120 (Visit

11), Week 132 (Visit 12), Week 144 (Visit 13 - End-of-Treatment/Premature Discontinuation), and at the Post-Treatment visit (6 weeks post discontinuation of study drug).

Weight (in kg) will be measured at Screening/Baseline on Visit 1, Week 12 (Visit 2), Week 24 (Visit 3), Week 36 (Visit 4), Week 48 (Visit 5), Week 60 (Visit 6), Week 72 (Visit 7), Week 84 (Visit 8), Week 96 (Visit 9) Week 108 (Visit 10), Week 120 (Visit 11), Week 132 (Visit 12), Week 144 (Visit 13- End-of-Treatment/Premature Discontinuation), and at the Post-Treatment visit (6 weeks post discontinuation of study drug).

A full physical examination (including evaluation of cardiovascular system, chest and lungs, thyroid, abdomen, nervous system, skin and mucosae, musculoskeletal system, eyes, ears, nose, mouth, throat, spine, lymph nodes, extremities, and genitourinary) will be conducted at Screening/Baseline (Visit 1), Week 48 (Visit 5), and Week 96 (Visit 9) and Week 144 (Visit 13 – End of Treatment/Premature Discontinuation) visit.

Physical exams may also be performed at any time during the study as clinically indicated.

7.6. Hematology Laboratory Assessment

Hematology laboratory assessments will include white blood cell count with differential, hemoglobin, hematocrit, mean corpuscular volume, mean corpuscular hemoglobin, mean corpuscular hemoglobin concentration, total red cell count with morphology, and platelet count. These parameters will be measured at Screening/Baseline on Visit 1, Week 12 (Visit 2), Week 24 (Visit 3), Week 36 (Visit 4), Week 48 (Visit 5), Week 60 (Visit 6), Week 72 (Visit 7), Week 84 (Visit 8), Week 96 (Visit 9) Week 108 (Visit 10), Week 120 (Visit 11), Week 132 (Visit 12), Week 144 (Visit 13- End-of-Treatment/Premature Discontinuation), and at the Post-Treatment visit (6 weeks post discontinuation of study drug). Hematology parameters will be analyzed by the central laboratory. The Central Laboratory Manual should be consulted for collection, processing, and shipping details.

7.7. Serum Biochemistry Laboratory Assessment

Biochemistry laboratory assessments will include sodium, potassium, chloride, bicarbonate, blood urea nitrogen, creatinine, magnesium, calcium, phosphorus, uric acid, glucose, total protein, albumin, globulin, albumin:globulin ratio, bilirubin (total, direct and indirect), AST, ALT, GGT, CK, lactate dehydrogenase (LDH), alkaline phosphatase, total cholesterol, high-density lipoprotein (HDL), low-density lipoprotein (LDL), triglycerides, and cystatin C. These parameters will be measured at Screening/Baseline on Visit 1, Week 12 (Visit 2), Week 24 (Visit 3), Week 36 (Visit 4), Week 48 (Visit 5), Week 60 (Visit 6), Week 72 (Visit 7), Week 84 (Visit 8), Week 96 (Visit 9) Week 108 (Visit 10), Week 120 (Visit 11), Week 132 (Visit 12), Week 144 (Visit 13 - End-of-Treatment/Premature Discontinuation), and at the Post-Treatment visit (6 weeks post discontinuation of study drug). Patients should have fasted for at least 8 hours prior to blood collection. Biochemistry parameters will be analyzed by the central laboratory. The Central Laboratory Manual should be consulted for collection, processing, and shipping details.

7.8. Urinalysis

Urinalysis will include analysis for pH, specific gravity, glucose, ketones, blood, protein, urobilinogen, bilirubin, nitrite, and leukocytes. These parameters will be measured at

Screening/Baseline on Visit 1, Week 12 (Visit 2), Week 24 (Visit 3), Week 36 (Visit 4), Week 48 (Visit 5), Week 60 (Visit 6), Week 72 (Visit 7), Week 84 (Visit 8), Week 96 (Visit 9) Week 108 (Visit 10), Week 120 (Visit 11), Week 132 (Visit 12), Week 144 (Visit 13 - End-of-Treatment/Premature Discontinuation), and at the Post-Treatment visit (6 weeks post discontinuation of study drug). These parameters will be analyzed by the central laboratory. Urine samples will also be collected and shipped to central laboratory for assessment of urine protein, creatinine, osmolality, and urinalysis. The Central Laboratory Manual should be consulted for collection, processing, and shipping details.

7.9. Renal Ultrasound

An ultrasound to examine the kidneys and collecting system will be performed at Screening/Baseline (Visit 1), Week 48 (Visit 5), and Week 96 (Visit 9) and Week 144 (Visit 13— End of Treatment/Premature Discontinuation) visit. The ultrasound examination will be performed according to local standards and a final interpretation and report will be provided by a local qualified expert. The findings will be captured in source documents and with the CRF.

A follow-up renal ultrasound may also be performed at any time during the study as clinically indicated at the discretion of the investigator. The PTC medical monitor must be informed via e-mail that an additional renal ultrasound was obtained and the serious adverse event reporting process should be followed, if applicable.

7.10. 12-Lead ECG

A 12-lead ECG will be obtained at Screening/Baseline (Visit 1), Week 48 (Visit 5), Week 96 (Visit 9) Week 144 (Visit 13— End of Treatment/Premature Discontinuation) visit, and at the Post-Treatment Visit (6 weeks post discontinuation of study drug). The ECG will be performed and interpreted locally. The findings will be captured in source documents and with the CRF.

A follow-up ECG may also be performed at any time during the study as clinically indicated at the discretion of the investigator. The PTC medical monitor must be informed via e-mail that an additional ECG was obtained and the serious adverse event reporting process should be followed, if applicable.

7.11. Study Drug Administration

Patients should take study drug TID as described in [Section 6.2.2](#) Study drug supply sufficient for each 12-week treatment period will be supplied to the patient at Screening/Baseline (Visit 1), Week 12 (Visit 2), Week 24 (Visit 3), Week 36 (Visit 4), Week 48 (Visit 5), Week 60 (Visit 6), Week 72 (Visit 7), and Week 84 (Visit 8) Week 96 (Visit 9) Week 108 (Visit 10), Week 120 (Visit 11), Week 132 and Week 132 (Visit 12). Sufficient drug for 90 days (12 weeks + 6 days) will be provided at each of these visits so lessen the likelihood that patients will experience drug shortages due to inadvertent loss of some of the sachets or scheduling delays for return visits.

7.12. Study Drug Compliance

Study drug compliance will be assessed using a Study Drug Administration Record (to be completed by the investigational site pharmacist or delegate site staff), which will document the return of unused sachets for compliance assessments.

Patients or caregivers will return all unused sachets of study drug to the study site for full compliance assessments using the Study Drug Administration Record. Clinic staff will record the study drug dosing information including the actual clock time of each dose when the patient is dosed in the clinic.

7.13. Adverse Events

Adverse events must be assessed and documented at each clinic visit. This information will be collected at Screening/Baseline (Visit 1) – following initiation of study drug, Week 12 (Visit 2), Week 24 (Visit 3), Week 36 (Visit 4), Week 48 (Visit 5), Week 60 (Visit 6), Week 72 (Visit 7), Week 84 (Visit 8), Week 96 (Visit 9) Week 108 (Visit 10), Week 120 (Visit 11), Week 132 (Visit 12), Week 144 (Visit 13) and at the Post-Treatment Visit (6 weeks post discontinuation of study drug). In addition, patients/caregivers will be encouraged to report adverse events of concern at any time in the intervals between visits.

7.14. Concomitant Medications

Information regarding any concomitant medications administered, as well as information regarding all non-drug therapies, will be collected throughout the study. This information will be collected at Screening/Baseline (Visit 1) – following initiation of study drug, Week 12 (Visit 2), Week 24 (Visit 3), Week 36 (Visit 4), Week 48 (Visit 5), Week 60 (Visit 6), Week 72 (Visit 7), Week 84 (Visit 8), Week 96 (Visit 9) Week 108 (Visit 10), Week 120 (Visit 11), Week 132 (Visit 12), Week 144 (Visit 13) and at the Post-Treatment Visit (6 weeks post discontinuation of study drug).

7.15. 6-Minute Walk Test

Ambulation will be assessed via the 6MWT following standardized procedures (see Study Manual for detailed instructions). The 6MWT will be performed during Screening/Baseline on Visit 1, Week 12 (Visit 2), Week 24 (Visit 3), Week 36 (Visit 4), Week 48 (Visit 5), Week 60 (Visit 6), Week 72 (Visit 7), Week 84 (Visit 8), and Week 96 (Visit 9) Week 108 (Visit 10), Week 120 (Visit 11), Week 132 (Visit 12), Week 144 (Visit 13- End-of-Treatment/Premature Discontinuation).

7.16. Timed Function Tests

Timed function tests will be performed and will include the time taken to run/walk 10 meters, time to stand from a supine position, time to climb 4 stairs, and time to descend 4 stairs [Mendell 1989, Griggs 1991, Beenakker 2005a, Pradhan 2006] (see Study Manual for detailed instructions). These parameters will be monitored at Screening/Baseline on Visit 1, Week 12 (Visit 2), Week 24 (Visit 3), Week 36 (Visit 4), Week 48 (Visit 5), Week 60 (Visit 6), Week 72 (Visit 7), Week 84 (Visit 8), and Week 96 (Visit 9) Week 108 (Visit 10), Week 120 (Visit 11), Week 132 (Visit 12), Week 144 (Visit 13- End-of-Treatment/Premature Discontinuation).

7.17. North Star Ambulatory Assessment

The NSAA will be used to evaluate physical function, using standardized procedures (see Study Manual for detailed instructions). The NSAA will be performed at Screening/Baseline on Visit 1, Week 12 (Visit 2), Week 24 (Visit 3), Week 36 (Visit 4), Week 48 (Visit 5), Week 60

(Visit 6), Week 72 (Visit 7), Week 84 (Visit 8), and Week 96 (Visit 9) Week 108 (Visit 10), Week 120 (Visit 11), Week 132 (Visit 12), Week 144 (Visit 13-End-of-Treatment/Premature Discontinuation).

7.18. Performance of Upper Limb Assessment (PUL)

The PUL assessment will be performed to evaluate upper limb function. The PUL assessment will be performed at Screening/Baseline on Visit 1, Week 12 (Visit 2), Week 24 (Visit 3), Week 36 (Visit 4), Week 48 (Visit 5), Week 60 (Visit 6), Week 72 (Visit 7), Week 84 (Visit 8), and Week 96 (Visit 9) Week 108 (Visit 10), Week 120 (Visit 11), Week 132 (Visit 12), Week 144 (Visit 13- End-of-Treatment/Premature Discontinuation).

7.19. Activities of Daily Living/Disease Symptom Survey

A survey will be administered at Screening/Baseline on Visit 1, Week 12 (Visit 2), Week 24 (Visit 3), Week 36 (Visit 4), Week 48 (Visit 5), Week 60 (Visit 6), Week 72 (Visit 7), Week 84 (Visit 8), and Week 96 (Visit 9) Week 108 (Visit 10), Week 120 (Visit 11), Week 132 (Visit 12), Week 144 (Visit 13- End-of-Treatment/Premature Discontinuation) to collect prospective information on patient and/or parent-reported changes in activities of daily living and disease symptoms. The survey will be available in all languages relevant for this study and will be administered by the site staff to the parent/caregiver and/or patient.

7.20. PODCI Questionnaire

HRQL will be measured via the Pediatric Outcomes Data Collection Instrument (PODCI) domains of Transfers/Basic Mobility and Sports/Physical Functioning. The PODCI questionnaire will be available in all languages relevant for this study and will be completed by the parent/caregiver. If possible, the same parent/caregiver should complete the questionnaire each time. The PODCI questionnaire will be completed during Screening/Baseline on Visit 1, Week 12 (Visit 2), Week 24 (Visit 3), Week 36 (Visit 4), Week 48 (Visit 5), Week 60 (Visit 6), Week 72 (Visit 7), Week 84 (Visit 8), and Week 96 (Visit 9) Week 108 (Visit 10), Week 120 (Visit 11), Week 132 (Visit 12), Week 144 (Visit 13 - End-of-Treatment/Premature Discontinuation). Please refer to the Study Manual for further details on how to administer the PODCI questionnaire.

7.21. Spirometry

Spirometry will be conducted in a standardized fashion (see Study Manual for details) and will be performed at Screening/Baseline on Visit 1, Week 24 (Visit 3), Week 48 (Visit 5), Week 72 (Visit 7), and Week 96 (Visit 9), Week 120 (Visit 11), Week 144 (Visit 13- End-of-Treatment/Premature Discontinuation).

7.22. Blood for Analysis of Pharmacokinetics

Blood for trough ataluren concentrations will be collected at Week 12 (Visit 2), Week 24 (Visit 3), Week 36 (Visit 4), Week 48 (Visit 5), Week 60 (Visit 6), Week 72 (Visit 7), Week 84 (Visit 8), and Week 96 (Visit 9) Week 108 (Visit 10), Week 120 (Visit 11), Week 132 (Visit 12), Week 144 (Visit 13-End-of-Treatment/Premature Discontinuation immediately prior to the morning

dose of study drug. The Central Laboratory Manual should be consulted for collection, processing, and shipping details.

Samples will be stored at the bioanalytical lab for analysis of ataluren parent drug using a validated high performance liquid chromatography with tandem mass spectrometry (HPLC/MS-MS) method. Thereafter, samples will be retained at the bioanalytical lab for potential follow-up analyses of ataluren metabolites or corticosteroid parent drug and metabolites.

7.23. Blood Collection Summary

Information regarding the types and approximate amounts of blood samples to be collected in the study is provided in Table 4. Assuming a 144-week treatment of ataluren, the maximum amount of blood to be drawn at a visit is ~12 mL and the total amount of blood to be drawn over the entire 144-week study period (including the Screening visit, the 96-week treatment period, and the 6-week follow-up period) is approximately 152 mL.

Table 4. Blood Drawing Requirements

Test	Sample Type	Tube Type	Tube Top (Color)	Tube Size (mL)	Blood Per Tube (mL)	Number of Tubes		Total Blood (mL)
						Per Visit	Total	
Hematology	Whole blood	EDTA	Lavender	3	3	1	14	42
Biochemistry	Serum	Clot	Gold	5	5	1	14	70
Blood for trough PK	Plasma	K ₃ -EDTA	Lavender	4	4	1	10	40
Maximum Total								152

Abbreviations: K₃ = tripotassium, EDTA = ethylenediaminetetraacetate

8. ADVERSE EVENT ASSESSMENTS

8.1. Adverse Event Definitions

8.1.1. Adverse Events

An adverse event is any untoward medical occurrence associated with the use of a drug (investigational medicinal product) in humans, whether or not it is considered related to the drug. An adverse event can therefore be any unfavorable and unintended sign (including an abnormal laboratory finding), symptom, or disease in a study patient who is administered study drug in this study.

For this protocol, untoward medical occurrences that should be reported as adverse events include the following:

- All adverse events that are suspected to be due to study drug.
- Overdose (administration of a study drug dose >4 times the highest intended total daily dose level for this protocol [>160 mg/kg/day]) of study drug.
- All reactions from medication misuse, abuse, withdrawal, sensitivity, or toxicity.

- All reactions that result from medication errors or uses of the study drug outside what is described in the protocol.
- Apparently unrelated illnesses, including the worsening of a preexisting illness.
- Injury or accidents. Note that if a medical condition is known to have caused the injury or accident (a fall secondary to dizziness), the medical condition (dizziness) and the accident (fall) should be reported as 2 separate adverse events. The outcome of the accident (hip fracture secondary to the fall) should be recorded in source documents.
- Abnormalities in physiological testing or physical examination findings that require clinical intervention or further investigation (beyond ordering a repeat [confirmatory] test).
- Laboratory or ECG abnormalities that require clinical intervention or further investigation (beyond ordering a repeat [confirmatory] test) unless they are associated with an already reported clinical event. Laboratory abnormalities associated with a clinical event (eg, elevated liver enzymes in a patient with jaundice) should be captured in the source documents. Laboratory abnormalities not requiring clinical intervention or further investigation will be captured as part of overall laboratory monitoring, and should not be reported as adverse events.
- A preexisting condition (eg, allergic rhinitis) must be noted on the appropriate electronic CRF (eCRF) for Visit 1, but should not be reported as an adverse event unless the condition worsens or episodes increase in frequency during the adverse event reporting period. Diagnostic and therapeutic non-invasive and invasive procedures, such as surgery, should not be reported as adverse events. However, the medical condition for which the procedure was performed should be reported if it meets the definition of an adverse event. For example, an acute appendicitis that begins during the adverse event reporting period should be reported as the adverse event and the resulting appendectomy should be recorded in the source documents. If a surgical procedure was planned prior to entry into the study, and the surgery is not performed because of a worsening of a baseline condition, this should not be reported as an adverse event. Note that, as described in Section 8.1.2, any inpatient hospitalization occurring as the consequence of an adverse event during the study period should be reported as an SAE.

Each adverse event is to be classified as serious or nonserious by the investigator using medical and scientific judgment.

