3.3. Clinical Endpoints

Primary

- Safety profile characterized by type, frequency, severity, timing, and relationship to ataluren of any adverse events or laboratory abnormalities

Secondary

Physical

- Change in ambulation as measured by the 6MWT
- Change in proximal muscle function as assessed by timed function tests (time to rise from supine position, time to run 10 meters, and time to climb/descend 4 stairs)
- Change in physical function as assessed by the North Star Ambulatory Assessment

- Change in motor performance of the upper limb as measured by the Performance Upper Limb (PUL)

Pulmonary function

Change in pulmonary function as measured by spirometry (eg. FVC, FEV1)

Patient-Reported Outcomes

- Change in patient- and parent/caregiver-reported HRQL as measured by the PODCI Transfer/Basic Mobility and Sports/Physical Functioning scores
- Change in patient and parent/caregiver reported activities of daily living

Exposure

- Pre-dose ataluren plasma concentrations prior to morning ataluren administration at each clinic visit as assessed by a validated bioanalytical method

Safety

- Change from baseline in other safety parameters (eg, vital signs)

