8.3. Adverse Event Recording

All adverse events (both serious and nonserious) that occur in patients during the adverse event reporting period must be recorded, whether or not the event is considered drug related. In addition, any known untoward event that occurs subsequent to the adverse event reporting period that the investigator assesses as possibly related to the investigational drug/product should also be recorded as an adverse event.

All adverse events are to be recorded in the source documents and on the CRF using concise medical terminology; whenever possible terms contained in Medical Dictionary for Regulatory Activities (MedDRA) should be employed. In addition, the following information should be recorded:

- Indication of whether the event is serious or nonserious (see [Section 8.1.2](#))
- Relationship to study drug (see [Section 8.4](#))
- Severity of the event (see [Section 8.5](#))
- Onset date
- Resolution date, or date of death
- Action taken
- Outcome of the event

Classification of the event as serious or nonserious determines the reporting procedures to be followed.

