Patients who experience limb fractures should have fixation as directed by an orthopedic surgeon. Patients who develop vertebral fractures can be treated with bisphosphonates (eg, pamidronate, 0.5 to 1 mg/kg/day intravenously for 3 days every 4 months). Patients should not have a corticosteroid dosage adjustment due to the occurrence of fractures.

Cataracts

The development of cataracts should prompt referral to an ophthalmologist for evaluation. Patients should not have a corticosteroid dosage adjustment due to the occurrence of cataracts.

Cushingoid Appearance

If the patient develops a Cushingoid appearance, that is unacceptable to the patient/family, the following actions are recommended:

- Corticosteroid dosage should not be increased to adjust for increases in body weight
- Reassurance and support should be provided. Counseling from a child psychologist should be considered.
- If the Cushingoid appearance remains unacceptable to child/family, dosage reductions of ≤ 5 mg total dose for prednisone (≤ 6 mg total dose for deflazacort) at ~6-8-week intervals can be considered.
- Every attempt should be made to avoid stopping corticosteroids solely for Cushingoid appearance; if the patient/family demands that corticosteroids be stopped, see [Section D](#) below for procedures for withdrawal of corticosteroids.

Gastrointestinal Irritation

In the event of the development of symptoms consistent with esophagitis, gastritis, or duodenitis, the following interventions are recommended:

- Treatment with supportive care (H_2 antagonists, proton pump inhibitors, antacids) should be initiated and corticosteroid dosage should not be increased to adjust for increases in body weight.
- If symptoms persist for ≥ 6 weeks despite supportive care (H_2 antagonists, proton pump inhibitors, antacids), a gastroenterology consultation should be obtained.
- If symptoms persist despite continued supportive care (H_2 antagonists, proton pump inhibitors, antacids) and gastroenterology evaluation, dosage reductions of ≤ 5 mg total dose for prednisone (≤ 6 mg total dose for deflazacort) at ~6-8-week intervals can be considered.
- If the gastroenterologist recommends discontinuation of corticosteroids for frank gastrointestinal ulceration, bleeding, etc, corticosteroids may be stopped. See [Section D](#) below for procedures for withdrawal of corticosteroids.

Height Gain Inhibition

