## 5.7. Primary Variables

### 5.7.1. Adverse Events

Adverse events will be classified using MedDRA version 20.1 classification system. The severity of adverse events will be graded by the investigator according to the CTCAE, Version 3.0 whenever possible. A treatment-emergent adverse event (TEAE) is defined as an adverse event that occurs or worsens in the period extending from the day of a subject's first dose of study drug to 6 weeks after the last dose of study drug in this study.

If a subject has multiple events under any given SOC and PT, the subject will be counted only once under that SOC and PT. If a subject has the same AE on multiple occasions, the highest severity (fatal, life-threatening, severe, moderate, and mild) recorded for the event will be presented and the highest drug relationship (1 = 'Unrelated', 2 = 'Unlikely', 3 = 'Possibly', 4 = 'Probably', 5 = 'Related'), reclassified into Related ('Possibly Related', 'Probably Related', 'Related') or Not Related ('Unrelated' and 'Unlikely'), will be presented on the respective tables.

Total numbers of AEs, TEAEs and serious AEs (SAE) and the number and percentage of subjects experiencing  $\geq 1$  TEAE,  $\geq 1$  SAE, discontinuation due to AE, and death will be tabulated. The number and percentage of subjects with TEAEs and SAEs will be by relationship to study drug and CTCAE/severity, respectively.

The number and percentage of subjects experiencing a specific TEAE will be tabulated

- 1) by SOC, and PT
- 2) by SOC, PT, and CTCAE/severity grade
- 3) by SOC in the descending order of the SOC frequency overall group,
- 4) by PT in the descending order of the PT frequency in overall group.

The following TEAEs will be analyzed similarly:

- 1) by SOC, and PT and

- 2) by SOC, PT, and CTCAE/severity grade.
- Possibly or probably treatment-related TEAEs
  - Serious TEAEs and possibly or probably treatment-related serious TEAEs
  - TEAEs leading to discontinuation from treatment
  - Adrenal, hepatic and renal events leading to special diagnostic evaluations TEAEs and possibly or probably treatment-related hepatic and renal TEAEs leading to special diagnosis evaluation
  - TEAEs with CTCAE/severity grade  $\geq 3$  and possibly or probably treatment-related TEAEs with CTCAE/severity grade  $\geq 3$
  - Common TEAEs (subject frequency of  $\geq 5\%$ )

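### Protocol 8.1.1 contradicts itself on injuries from accidents, so fractures after falls may be missing or inconsistently coded in the adverse-event tables

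*Protocol*

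**What the plan says.** The primary endpoint (Protocol 3.3, repeated in SAP 3.3) is: "Safety profile characterized by type, frequency, severity, timing, and relationship to ataluren of any adverse events or laboratory abnormalities".

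Protocol 8.1.1 lists what sites should report as adverse events. One bullet opens with "Injury or accidents". Its note covers the case where a medical condition is known to have caused the accident, using a boy who falls because he is dizzy: "the medical condition (dizziness) and the accident (fall) should be reported as 2 separate adverse events". The next sentence deals with what the fall led to: "The outcome of the accident (hip fracture secondary to the fall) should be recorded in source documents".

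Protocol 8.3 gives the general recording rule: "All adverse events are to be recorded in the source documents and on the CRF using concise medical terminology".

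On the analysis side, SAP 5.1 builds by-patient listings from CRF modules. SAP 5.7.1 tabulates TEAEs by system organ class and preferred term, with severity and relationship taken from the recorded event.

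**The concern.** A fracture is an injury, so the opening of the bullet makes it reportable. The worked example in the same bullet points the other way. Two sites could handle the same fracture differently and both claim to have followed the protocol.

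Type and severity are named components of the primary endpoint. If a fracture exists in the database only as a fall, the type is wrong and any grade or causality judgement attaches to the fall. The population makes this more than a technicality: Protocol 2.1 says that by age 8 most of these boys often fall while walking, and Protocol 13.2.11 names osteoporosis as a side effect of the corticosteroids that many of them take. A fracture can also interrupt walking. Without a coded record of it, an abrupt drop in 6-minute walk distance, or a loss of ambulation under SAP 5.8.4, is harder to interpret.

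**Working it through.** No arithmetic in the plan bears on this point, so the check sets the provisions side by side.

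**1. What the example counts.** It has three elements: dizziness, fall and hip fracture. Two are to be reported as adverse events, and the text gives that number. The third is sent to source documents. The note treats the fall as the injury or accident and the fracture as its outcome, so a site has no prompt to read the fracture back into the opening words of the bullet.

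**2. How 8.1.1 uses the same direction elsewhere.** It does so twice, both times for items that are not separate adverse events:
- Laboratory abnormalities tied to an already reported clinical event.
- A procedure: the appendicitis "should be reported as the adverse event and the resulting appendectomy should be recorded in the source documents".

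By contrast, 8.3 sends adverse events to source documents and to the CRF. The natural reading of the fracture sentence is therefore that no separate adverse-event record is made.

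**3. Provisions that point towards reporting.**
- The opening of the same bullet covers injuries.
- 8.1.1 makes examination findings that need intervention or investigation reportable, and SAP 5.8.11 assumes that abnormal examination findings are reported.
- 8.1.1 says that the condition behind a procedure is reportable if it meets the adverse-event definition. Appendix A expects orthopedic fixation of limb fractures.
- Appendix A places osteoporotic fractures among corticosteroid-related adverse events.
- 8.1.1 and 8.1.2 make admission resulting from an adverse event an SAE.

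These show a contradiction. They do not show which instruction a site followed.

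**4. Whether the backstops recover the fracture as a coded term.**
- *SAE route.* 8.1.2 does not count emergency-room care without admission, or observation there for under 24 hours, as serious. A fracture managed that way need not become an SAE unless someone judges it medically important. If it does, 8.9 asks for the same term on the CRF and the SAE form, so the SAE may also read *fall*.
- *Non-drug therapies.* These are collected (Protocol 7.14) and coded (SAP 5.5). They may reveal a treatment, but not a graded and attributed event.
- *Patient- and caregiver-reported outcomes.* Protocol 10.4.3 says that these will not be reconciled with adverse events.
- *SAP.* It has no rule for retrieving events from source documents.

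**5. Size.** Let *N* be the number enrolled, *r* the proportion with a fracture after a fall, and *s* the share of those boys with no fracture term in the adverse-event data. The number affected is *N* × *r* × *s*. Protocol 10.1 bounds *N* at about 220. The documents give no value for *r*. The share *s* runs from 0 (every site reports the fracture as an injury) to 1 (every site follows the example literally). No count can be derived.

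**The case against.** The strongest reply is that the sentence does not exclude the CRF. It says nothing about source documents being the sole place of record, and 8.3 sends every adverse event to both. Where 8.1.1 means to exclude something, as with procedures or laboratory values needing no action, it says so outright. The note is also limited to accidents with a known medical cause, so a boy who simply trips may fall outside it. The severity rule in 8.5 asks for the highest grade attained, so a fall with a fracture need not be graded as trivial. Appendix A concerns corticosteroid management, for example "Patients should not have a corticosteroid dosage adjustment due to the occurrence of fractures", and contains no rule on adverse-event recording.

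Much of this stands. Exclusion is an inference, the reach of the note is unclear, and Appendix A supports reporting fractures rather than suppressing them. What does not follow is that the wording is harmless. The stated count of two events does the excluding, the parallel uses in 8.1.1 support that reading, and uncertainty about the note's reach is a further source of inconsistency between sites.

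A reader might infer that fractures after falls *are* missing from the primary endpoint, or that every SAP safety table is affected. The documents support neither. Under-recording is possible but not shown, and the laboratory, vital-sign, ECG and renal-ultrasound summaries do not depend on adverse-event terms.

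**Conclusion.** The concern holds as an internal inconsistency with a plausible route to under-recording. Read naturally, the example leaves a fracture after a fall without its own term, grade or seriousness. Such fractures may then be missing or inconsistently coded in the TEAE tables. The fall remains reported, and fractures leading to admission should surface as SAEs, possibly under another term.

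The share affected lies between 0% and 100% of such fractures and cannot be narrowed from the documents. It is tempting to apply an assumed fracture rate to 220 boys over 144 weeks and present the product as the number lost. That would overstate what is known. The figure of 220 is the expected enrolment of the parent study, SAP 5.2 and Section 7 record that the sponsor ended the extension early, and the product would assume that every site omitted every fracture.

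Neither document names a fracture rate as an endpoint, and the study tests no formal hypothesis. The point is worth correcting because it sits in the definition that feeds the primary endpoint and cannot be repaired at analysis without returning to source documents.

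**What to change.** Amend the sentence in Protocol 8.1.1, or the adverse-event CRF completion guideline, so that a clinically distinct injury resulting from an accident is entered on the adverse-event CRF as its own event, with its own grade and seriousness, and linked to the accident. State that this applies whether or not a medical condition caused the accident.

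Before database lock, query source documents for every adverse event coded as a fall or accident, and add any such injury not already recorded. If the database is already locked, state the recording rule as a limitation beside any fracture frequency that is reported.

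SAP 5.7.1 needs no new method, since the added events would appear under their own preferred terms. The cost is one sentence, a modest targeted query, a few more adverse-event records and a slightly less favourable adverse-event count.
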